#### Metastatic Melanoma

In patients receiving ipilimumab 3 mg/kg in Trial 1, severe, life-threatening, or fatal (diarrhea of 7 or more stools above baseline, fever, ileus, peritoneal signs; Grade 3 to 5) immune-mediated enterocolitis occurred in 34 ipilimumab-treated patients (7%), and moderate (diarrhea with up to 6 stools above baseline, abdominal pain, mucus or blood in stool; Grade 2) enterocolitis occurred in 28 ipilimumab -treated patients (5%). Across all ipilimumab-treated patients (n=511), 5 patients (1%) developed intestinal perforation, 4 patients (0.8%) died as a result of complications, and 26 patients (5%) were hospitalized for severe enterocolitis.

The median time to onset of Grade 3 to 5 enterocolitis was 1.7 months (range: 11 days to 3.1 months) and for Grade 2 enterocolitis was 1.4 months (range: 2 days to 4.3 months).

#### Immune-Mediated Hepatitis

Immune-mediated hepatitis, including fatal cases, can occur with ipilimumab.

Monitor liver function tests (hepatic transaminase and bilirubin levels) and assess patients for signs and symptoms of hepatotoxicity before each dose of ipilimumab. In patients with hepatotoxicity, rule out infectious or malignant causes and increase frequency of liver function test monitoring until resolution.

Permanently discontinue ipilimumab in patients with Grade 3 to 4 hepatotoxicity and administer systemic corticosteroids at a dose of 1 to 2 mg/kg/day of prednisone or equivalent. When liver function tests show sustained improvement or return to baseline, initiate corticosteroid tapering and continue to taper over 1 month. Across the clinical development program for ipilimumab, mycophenolate treatment has been administered in patients who have persistent severe hepatitis despite high-dose corticosteroids. Withhold ipilimumab in patients with Grade 2 hepatotoxicity.

#### Metastatic Melanoma

In patients receiving ipilimumab 3 mg/kg in Trial 1, severe, life-threatening, or fatal hepatotoxicity (AST or ALT elevations of more than 5 times the upper limit of normal or total bilirubin elevations more than 3 times the upper limit of normal; Grade 3 to 5) occurred in 8 ipilimumab-treated patients (2%), with fatal hepatic failure in 0.2% and hospitalization in 0.4% of ipilimumab-treated patients. An additional 13 patients (2.5%) experienced moderate hepatotoxicity manifested by liver function test abnormalities (AST or ALT elevations of more than 2.5 times but not more than 5 times the upper limit of normal or total bilirubin elevation of more than 1.5 times but not more than 3 times the upper limit of normal; Grade 2). The underlying pathology was not ascertained in all patients but in some instances included immune- mediated hepatitis. There were insufficient numbers of patients with biopsy-proven hepatitis to characterize the clinical course of this event.

## Immune-Mediated Dermatitis

Immune-mediated dermatitis, including fatal cases, can occur with ipilimumab.

Monitor patients for signs and symptoms of dermatitis, such as rash and pruritus. Unless an alternate etiology has been identified, signs or symptoms of dermatitis should be considered immune-mediated.

Permanently discontinue ipilimumab in patients with Stevens-Johnson syndrome, toxic epidermal necrolysis, or rash complicated by full thickness dermal ulceration, or necrotic, bullous, or hemorrhagic manifestations. Administer systemic corticosteroids at a dose of 1 to 2 mg/kg/day of prednisone or equivalent. When dermatitis is controlled, corticosteroid tapering should occur over a period of at least 1 month. Withhold ipilimumab dosing in patients with moderate to severe signs and symptoms [see Dosage and Administration (2.3)].

For mild to moderate dermatitis, such as localized rash and pruritus, treat symptomatically. Administer topical or systemic corticosteroids if there is no improvement of symptoms within 1 week.

### Metastatic Melanoma

In patients receiving ipilimumab 3 mg/kg in Trial 1, severe, life-threatening, or fatal immune-mediated dermatitis (e.g., Stevens-Johnson syndrome, toxic epidermal necrolysis, or rash complicated by full thickness dermal ulceration, or necrotic, bullous, or hemorrhagic manifestations; Grade 3 to 5) occurred in 13 ipilimumab-treated patients (2.5%). One patient (0.2%) died as a result of toxic epidermal necrolysis and one additional patient required hospitalization for severe dermatitis. There were 63 patients (12%) with moderate (Grade 2) dermatitis.

The median time to onset of moderate, severe, or life-threatening immune-mediated dermatitis was 22 days and ranged up to 4.0 months from the initiation of ipilimumab.

Seven ipilimumab-treated patients (54%) with severe dermatitis received high-dose corticosteroids (median dose 60 mg prednisone/day or equivalent) for up to 3.4 months followed by corticosteroid taper. Of these 7 patients, 6 had complete resolution; time to resolution ranged up to 3.6 months.

Of the 63 patients with moderate dermatitis, 25 (40%) were treated with systemic corticosteroids (median of 60 mg/day of prednisone or equivalent) for a median of 15 days, 7 (11%) were treated with only topical corticosteroids, and 31 (49%) did not receive systemic or topical corticosteroids. Forty-four patients (70%) with moderate dermatitis were reported to have complete resolution, 7 (11%) improved to mild (Grade 1) severity, and 12 (19%) had no reported improvement.

## Immune-Mediated Neuropathies

Immune-mediated neuropathies, including fatal cases, can occur with ipilimumab.

Monitor for symptoms of motor or sensory neuropathy such as unilateral or bilateral weakness, sensory alterations, or paresthesia. Permanently discontinue ipilimumab in patients with severe neuropathy (interfering with daily activities) such as Guillain-Barré-like syndromes. Institute medical intervention as appropriate for management of severe neuropathy. Consider initiation of systemic corticosteroids at a dose of 1 to 2 mg/kg/day prednisone or equivalent for severe neuropathies. Withhold ipilimumab dosing in patients with moderate neuropathy (not interfering with daily activities) [see Dosage and Administration (2.3)].

## Metastatic Melanoma

In patients receiving ipilimumab 3 mg/kg in Trial 1, 1 case of fatal Guillain-Barré syndrome and 1 case of severe (Grade 3) peripheral motor neuropathy were reported. Across the clinical development program of ipilimumab, myasthenia gravis and additional cases of Guillain-Barré syndrome have been reported.

### Immune-Mediated Endocrinopathies

Immune-mediated endocrinopathies, including life-threatening cases, can occur with ipilimumab.

Monitor patients for clinical signs and symptoms of hypophysitis, adrenal insufficiency (including adrenal crisis), and hyper- or hypothyroidism. Patients may present with fatigue, headache, mental status changes, abdominal pain, unusual bowel habits, and hypotension, or nonspecific symptoms which may resemble other causes such as brain metastasis or underlying disease. Unless an alternate etiology has been identified, signs or symptoms of endocrinopathies should be considered immune-mediated.

Monitor clinical chemistries, adrenocorticotrophic hormone (ACTH) level, and thyroid function tests at the start of treatment, before each dose, and as clinically indicated based on symptoms. In a limited number of patients, hypophysitis was diagnosed by imaging studies through enlargement of the pituitary gland.

Withhold ipilimumab dosing in symptomatic patients and consider referral to an endocrinologist. Initiate systemic corticosteroids at a dose of 1 to 2 mg/kg/day of prednisone or equivalent, and initiate appropriate hormone replacement therapy [see Dosage and Administration (2.3)].

## Metastatic Melanoma

In patients receiving ipilimumab 3 mg/kg in Trial 1, severe to life-threatening immune-mediated endocrinopathies (requiring hospitalization, urgent medical intervention, or interfering with activities of daily living; Grade 3 to 4) occurred in 9 ipilimumab-treated patients (1.8%). All 9 patients had hypopituitarism and some had additional concomitant endocrinopathies such as adrenal insufficiency, hypogonadism, and hypothyroidism. Six of the 9 patients were hospitalized for severe endocrinopathies. Moderate endocrinopathy (requiring hormone replacement or medical intervention; Grade 2) occurred in 12 patients (2.3%) and consisted of hypothyroidism, adrenal insufficiency, hypopituitarism, and 1 case each of hyperthyroidism and Cushing's syndrome. The median time to onset of moderate to severe immune-mediated endocrinopathy was 2.5 months and ranged up to 4.4 months after the initiation of ipilimumab.

Of the 21 patients with moderate to life-threatening endocrinopathy, 17 patients required long-term hormone replacement therapy including, most commonly, adrenal hormones (n=10) and thyroid hormones (n=13).

### Other Immune-Mediated Adverse Reactions, Including Ocular Manifestations

Permanently discontinue ipilimumab for clinically significant or severe immune-mediated adverse reactions. Initiate systemic corticosteroids at a dose of 1 to 2 mg/kg/day prednisone or equivalent for severe immune-mediated adverse reactions.

Administer corticosteroid eye drops to patients who develop uveitis, iritis, or episcleritis. Permanently discontinue ipilimumab for immune-mediated ocular disease that is unresponsive to local immunosuppressive therapy [see Dosage and Administration (2.3)].

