**Table 3 Ipilimumab Dose Modification Guidelines for Drug-Related Adverse Events**

Toxicity	Hold For Grade	Timing for Restarting Treatment	Treatment Discontinuation
Diarrhea/Colitis	2	Toxicity resolves to Grade 0-1	Toxicity does not resolve within 12 weeks of last dose or inability to reduce corticosteroid to 10 mg or less of prednisone or equivalent per day within 12 weeks. Patients are to be treated with 1 mg/kg prednisone or equivalent if grade 2 or greater toxicity and tapered over several weeks
	3-4	Permanently discontinue	Permanently discontinue
AST, ALT, or Increased Bilirubin	2	Toxicity resolves to Grade 0-1	Toxicity does not resolve within 12 weeks of last dose
	3-4	Permanently discontinue (see exception below) a	Permanently discontinue
Type 1 diabetes mellitus (if new onset) or Hyperglycemia	T1DM or 3-4	Hold ipilimumab for new onset Type 1 diabetes mellitus or Grade 3-4 hyperglycemia associated with evidence of beta cell failure	Discontinue permanently
Hypophysitis	2-4	Toxicity resolves to Grade 0-1. Therapy with pembrolizumab can be continued while endocrine replacement therapy is instituted	Toxicity does not resolve within 12 weeks of last dose or inability to reduce corticosteroid to 10 mg or less of prednisone or equivalent per day within 12 weeks
Hyperthyroidism	3	Toxicity resolves to Grade 0-1	Toxicity does not resolve within 12 weeks of last dose or inability to reduce corticosteroid to 10 mg or less of prednisone or equivalent per day within 12 weeks
	4	Permanently discontinue	Permanently discontinue
Hypothyroidism		Therapy with ipilimumab can be continued while thyroid replacement therapy is instituted	Therapy with ipilimumab can be continued while thyroid replacement therapy is instituted
Infusion Reaction	2 b	Toxicity resolves to Grade 0-1	Permanently discontinue if toxicity develops despite adequate premedication
	3-4	Permanently discontinue	Permanently discontinue
Pneumonitis	2	Toxicity resolves to Grade 0-1	Toxicity does not resolve within 12 weeks of last dose or inability to reduce corticosteroid to 10 mg or less of prednisone or equivalent per day within 12 weeks
	3-4	Permanently discontinue	Permanently discontinue
Renal Failure or Nephritis	2	Toxicity resolves to Grade 0-1	Toxicity does not resolve within 12 weeks of last dose or inability to reduce corticosteroid to 10 mg or less of prednisone or equivalent per day within 12 weeks
	3-4	Permanently discontinue	Permanently discontinue

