Toxicity	Hold For Grade	Timing for Restarting Treatment	Treatment Discontinuation
All Other Drug-Related Toxicity c	3 or Severe	Toxicity resolves to Grade 0-1	Toxicity does not resolve within 12 weeks of last dose or inability to reduce corticosteroid to 10 mg or less of prednisone or equivalent per day within 12 weeks
	4	Permanently discontinue	Permanently discontinue

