**Table 7 Evaluating Adverse Events**

An investigator who is a qualified physician, will evaluate all adverse events as to:

V4.0 CTCAE Grading	Grade 1	Mild; asymptomatic or mild symptoms; clinical or diagnostic observations only; intervention not indicated.
	Grade 2	Moderate; minimal, local or noninvasive intervention indicated; limiting age-appropriate instrumental ADL.
	Grade 3	Severe or medically significant but not immediately life-threatening; hospitalization or prolongation or hospitalization indicated; disabling; limiting self-care ADL.
	Grade 4	Life threatening consequences; urgent intervention indicated.
	Grade 5	Death related to AE
Seriousness	A serious adverse event is any adverse event occurring at any dose or during any use of Merck product that:	
	† Results in death ; or	
	† Is life threatening ; or places the subject, in the view of the investigator, at immediate risk of death from the event as it occurred (Note: This does not include an adverse event that, had it occurred in a more severe form, might have caused death.); or	
	† Results in a persistent or significant disability/incapacity (substantial disruption of one's ability to conduct normal life functions); or	
	† Results in or prolongs an existing inpatient hospitalization (hospitalization is defined as an inpatient admission, regardless of length of stay, even if the hospitalization is a precautionary measure for continued observation. (Note: Hospitalization for an elective procedure to treat a pre-existing condition that has not worsened is not a serious adverse event. A pre-existing condition is a clinical condition that is diagnosed prior to the use of a Merck product and is documented in the patient's medical history.); or	
	† Is a congenital anomaly/birth defect (in offspring of subject taking the product regardless of time to diagnosis); or	
	Is a new cancer (that is not a condition of the study) (although not serious per ICH definition, is reportable to the Sponsor within 24 hours and to Merck within 2 working days to meet certain local requirements); or	

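### Section 4.2.5 ends ipilimumab for severe neuropathy, SJS/TEN or complicated rash, and other significant immune-mediated reactions, but Table 3's catch-all row, as printed, allows restart

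*Combined protocol and SAP*

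**What the plan says.** Section 4.2.5 (ipilimumab safety information) gives these stopping instructions:

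- Neuropathy: "Permanently discontinue ipilimumab in patients with severe neuropathy (interfering with daily activities"), with Guillain-Barré-like syndromes as the example.
- Skin: "Permanently discontinue ipilimumab in patients with Stevens-Johnson syndrome, toxic epidermal necrolysis, or rash complicated by full thickness dermal ulceration", or necrotic, bullous or hemorrhagic features. Other moderate to severe dermatitis is only withheld.
- Other immune-mediated reactions: "Permanently discontinue ipilimumab for clinically significant or severe immune-mediated adverse reactions". Ocular disease that does not respond to local immunosuppression is also a permanent stop. Neither instruction carries a CTCAE grade.
- Endocrinopathies: withhold in symptomatic patients, give steroids and replace hormones.

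Table 3 in Section 5.3.2 is the ipilimumab dose-modification table. Its named rows are colitis, liver tests, diabetes or hyperglycemia, hypophysitis, hyperthyroidism, hypothyroidism, infusion reaction, pneumonitis and renal events. Anything else belongs to "All Other Drug-Related Toxicity", which carries note marker c. That row holds at Grade 3 or severe and restarts at Grade 0-1. It stops permanently at Grade 4, or if the event has not resolved, or the steroid has not come down to 10 mg prednisone-equivalent or less, within 12 weeks. Section 5.3.2 sets no order of precedence between the table and Section 4.2.5.

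**The concern.** Both texts are written as instructions, and for the same event at the same severity they differ: one ends ipilimumab, the other pauses it. A clinician working from the dose table could re-dose after a recovered Grade 3 Guillain-Barré-like event or a recovered complicated rash. Section 4.2.5 reports a death from TEN and a fatal Guillain-Barré case on ipilimumab. Those deaths are not described as following re-dosing, and no fatal case is reported for the third group (other immune-mediated and ocular reactions). What is at stake is the safety of a small number of patients and consistent dosing across investigators. No endpoint or decision rule is affected.

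**Working it through.** **Step 1. The two texts side by side, as printed.**

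| Event | Section 4.2.5 | Table 3 | Result |
|---|---|---|---|
| Severe neuropathy, Grade 3 | Permanent stop | Catch-all: hold, restart at Grade 0-1 | Conflict |
| SJS, TEN, complicated rash, Grade 3 | Permanent stop | Catch-all: hold, restart at Grade 0-1 | Conflict |
| Either of the above, Grade 4 | Permanent stop | Catch-all: permanent stop | Agree |
| Other severe immune-mediated reaction with no row | Permanent stop | Catch-all: hold, restart at Grade 0-1 | Conflict |
| Clinically significant reaction or unresponsive ocular disease, below Grade 3 | Permanent stop, no grade given | Catch-all hold begins at Grade 3 or severe | Possible conflict |
| Uncomplicated severe dermatitis | Withhold | Catch-all: hold | Agree |
| Grade 3-4 colitis or liver toxicity | Permanent stop | Permanent stop; the liver entry reads "Permanently discontinue (see exception below") | Agree, subject to note a |

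**Step 2. Can these events be Grade 3?** Yes. Section 4.2.5 places the complicated rashes at Grade 3 to 5 and reports a severe motor neuropathy as Grade 3. Table 7 describes Grade 3 as "disabling; limiting self-care ADL", which fits a neuropathy that interferes with daily activities.

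**Step 3. Does another section settle it?**

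- Section 5.6.5 requires discontinuation for unacceptable adverse experiences and refers to Section 7.4. That section covers grading, seriousness and causality and lists no stopping events.
- Table 2 stops pembrolizumab for Grade 3 Guillain-Barré syndrome but sets no ipilimumab rule.
- Section 5.4.1 refers to Section 5.3 for dose modification, which leads back to Table 3.

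**Step 4. How often?** Event rates are given only for 3 mg/kg ipilimumab in Trial 1, n = 511. As a check on the denominator, 13/511 = 2.5%, which matches the reported rate of Grade 3-5 dermatitis. Intervals are Clopper-Pearson 95%.

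- Dermatitis: 13 Grade 3-5 cases minus 1 fatal = 12. 12/511 = 2.35% (1.22% to 4.07%). Times 43 = 1.01 patients (0.52 to 1.75). This is an upper figure, because it still contains Grade 4 cases, where the texts agree.
- Grade 3 neuropathy: 1/511 = 0.20% (0.005% to 1.09%). Times 43 = 0.08 patients (0.002 to 0.47).
- Other significant or severe reactions and ocular disease: the documents give no usable rate.

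**Step 5. Is a restart reachable?** Nominal ipilimumab days under Table 1 are 1, 22, 43 and 64.

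- Median onset of moderate or worse dermatitis is day 22. That median pools 63 Grade 2 with 13 Grade 3-5 cases, so 63/76 = 83% are Grade 2.
- Once dermatitis is controlled, "corticosteroid tapering should occur over a period of at least 1 month". If control came at onset and dosing waited for the taper, restart would be at about day 22 + 30 = 52, with one nominal dose (day 64) left. If control took more than 64 − 52 = 12 days, no nominal dose would remain.
- Seven patients with severe dermatitis received high-dose steroids. "Of these 7 patients, 6 had complete resolution; time to resolution ranged up to 3.6 months". At 30.4 days per month, 3.6 months is about 109 days, and the longest high-dose course of 3.4 months is about 103 days. Both exceed 12 weeks (84 days). The number who recovered within 12 weeks is not given.
- The 12-week limit itself ends on day 1 + 84 = 85 or day 22 + 84 = 106, after day 64. The protocol does not say whether held doses are made up.

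Re-dosing is therefore possible for an early event that resolves quickly. The documents do not show how likely it is.

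**The case against.** Section 4.2.5 reads like product-label background. It sits under Study Drugs, is headed as warnings and precautions, and cites label section numbers that do not correspond to this protocol. On that view Table 3 governs. Alternatively, a specific stop for SJS or Guillain-Barré-like events may be read as overriding a general catch-all. Either reading is reasonable, but the protocol states neither. If 4.2.5 is background only, the operating table has no printed permanent stop for a Grade 3 case that recovers in time, so the gap remains.

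Hold-and-restart at Grade 3 is a defensible default for non-immune toxicity. That stands, and the catch-all should keep that use. It is still notable that all five named non-endocrine rows (colitis, liver, infusion reaction, pneumonitis, renal) stop permanently at Grade 3-4, with liver subject to note a.

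The text of notes a to c is not in the available copy, which may be an extraction loss and not a fault of the plan. Note c could narrow the catch-all. This is a genuine caveat on the whole point.

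Investigator discretion under Sections 3.4 and 5.6.5 lowers the risk, but it does not say which rule applies.

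**Conclusion.** The inconsistency is real on the printed text and should be fixed. Confidence is medium because note c cannot be read. For neuropathy and complicated rash it is confined to Grade 3. For the ungraded clinically significant and ocular stops it may extend below Grade 3. The expected numbers are at most about 1 of 43 for complicated rash and about 0.1 of 43 for Grade 3 neuropathy. Both assume that 3 mg/kg monotherapy rates carry over to 1 mg/kg with pembrolizumab and aspirin, although Section 1.2.2 says ipilimumab dose affects adverse events.

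A reader might infer three stronger claims that the documents do not support:

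- That the protocol directs re-dosing after these events. Table 3 permits it on conditions, and the recovery times and the day-64 last dose may rule it out.
- That every severe skin or endocrine event is in conflict. Section 4.2.5 only withholds for uncomplicated severe dermatitis and for endocrinopathies.
- That every affected group includes a fatal case. Deaths are reported for rash and neuropathy only.

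**What to change.** Add Table 3 rows that permanently discontinue ipilimumab for:

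- (a) severe (Grade 3 or higher) neuropathy, including Guillain-Barré-like syndromes;
- (b) SJS, TEN, or rash with full-thickness ulceration or necrotic, bullous or hemorrhagic features;
- (c) other clinically significant or severe immune-mediated reactions without their own row, including ocular disease unresponsive to local therapy.

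Exclude uncomplicated severe dermatitis and endocrinopathies such as adrenal insufficiency from row (c), so that they stay at withhold as in Section 4.2.5. A row without that exclusion would create a new conflict. Keep the catch-all for non-immune toxicity. State in Section 5.3.2 that the amended Table 3 governs ipilimumab dosing, and say whether held doses are made up. Confirm that notes a to c are printed and agree with the new rows.

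The cost is amendment wording, with no added patients or procedures. The downside is that a few patients may receive fewer than four ipilimumab doses.

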## Metastatic Melanoma

In Trial 1, the following clinically significant immune-mediated adverse reactions were seen in less than 1% of ipilimumab-treated patients: nephritis, pneumonitis, meningitis, pericarditis, uveitis, iritis, and hemolytic anemia.

